[figure not shown]

Title: Preventing Weight Gain and Unhealthy Behaviors in Children

08/08/2019

Rigor and Transparency. The proposed study is designed to rigorously evaluate the effect of providing access to structured programs during the summer on children's unhealthy weight gain, fitness loss, and the obesogenic behaviors that underlie these effects. Specific examples of the rigor of this study include randomizing children following baseline measurement, using measures shown to produce valid and reliable data in the study population, completion of a power analysis, appropriate statistical analyses, properly controlled design, and blinding staff handling the data to study condition. These methods will allow for the proposed study to produce robust and unbiased results.

D1. Theoretical/Conceptual Framework - Structured Days Hypothesis. This study hypothesizes that summer camps will provide structure during the summer that will reduce children's obesogenic behaviors. Mechanisms driving reduced obesogenic behaviors on structured days are detailed in **Figure D1** below.

D2. Hypotheses.

Aim 1 (Primary): It is *hypothesized* that **A**) children randomized to attend the summer day camp will experience minimal gain in zBMI and loss of fitness during the summer that they receive summer camp access; **B**) children will experience accelerated weight gain and fitness loss during the summer they are randomized to not receive summer camp access and that **C**) all children will experience similar weight loss and fitness gain during the school year due to the restrictive, compulsory, and regulatory components of school.

Aim 2 (Secondary): It is *hypothesized* that **A**) children randomized to attend the camp will engage in fewer obesogenic behaviors during the summer that they attend the camp than their peers during the summer they do not attend camp, and that **B**) all children will engage in fewer and similar levels of obesogenic behaviors during the school year due to the restrictive, compulsory, and regulatory components of school.

Aim 3 (Exploratory): It is of interest to explore: **A**) if children randomized to attend the camp will experience increases in self-regulation while their peers who do not attend the camp will experience decreases in self-regulation, and if **B**) self-regulation at the beginning of summer will moderate unhealthy changes in weight and fitness at the end of the summer for those children who do not attend the summer camp.

D3. Study Design. The study will be a randomized controlled trial. To distribute costs over years, the study will recruit two cohorts of 1st and 3rd grade students. The first cohort will be recruited in Y01 and the second will be recruited in Y02. Following baseline data collection, children in each cohort will be randomly assigned to either the treatment or control. The sample of students recruited in the 1st grade will be observed during the summer after their 1st grade year and the school year when they are in the 2nd grade. Students recruited from the 3rd grade will be observed in the summer following their 3rd grade year and the school year during 4th grade.

D4. Study Population and Recruitment. Procedures for sampling children are detailed in **Clin-Trls Section 2, Recruitment and Retention Plan**. Briefly, the Recreation Commission operates 11 summer day camps located

at parks. Each camp serves ~100 children every summer. To draw a sample of children, 5 summer camps that operate in the catchment area of elementary schools where $\geq 90\%$ (range = 90%, 100%) of children enrolled are eligible for free and reduced lunch have been identified. A total of 2,333 children (49% female) attend these schools. Children attending the identified schools will be stratified by gender and grade level. In Y01 and Y02, 40 (i.e., 80 total) randomly identified children will be invited to participate in the study.

D5. Intervention to be Tested. A detailed description of the intervention to be tested can be found in Clin-Trls Section 4, Narrative Study Description and Interventions. Briefly, children in the study will be randomly identified to take part in the Voucher Program. During the summer, children in the Voucher Program will receive a voucher that covers enrollment fees associated with accessing a day camp operated at a park near their school. The total value of the voucher for a single child for an 8-week summer will be \$880 (\$110 per week). This fee covers all operating expenses plus transportation to and from the camp. The summer day camps (defined in **Section A5**) will be existing summer day camps operated by the Recreation Commission. The summer day camps provide indoor and outdoor opportunities for children to be physically active each day, provide enrichment and academic programming, as well as breakfast, lunch, and snacks. Importantly, these camps are enrolled in the USDA Summer Food Service Program. Thus, all meals adhere to the Summer Food Service Program nutrition guidelines. The camps employ 1 staff member for every 12 children and operate daily (Mon-Fri) for the entire summer. The camps open at 7am and close at 6 pm daily. Physical activity opportunities are scheduled for 3 to 4 hours each day, with the remaining 4 to 5 hours dedicated to enrichment or meals/snacks. These camps will operate according to routine practice, with no outside assistance from the investigative team. Children randomly assigned to the control group will be enrolled in the same schools as those randomized to receive the Voucher Program. The comparison/control group will not receive a voucher to attend a summer camp. It is possible that children serving in the control/comparison condition may elect to voluntarily participate in a summer program. However, based on enrollment numbers from pilot work (see **Section C**), the limited number of weeks children were enrolled (avg. of 2 weeks), the associated costs of enrolling (i.e., \$880 per child), and national data indicating that few children from low-income families attend summer day camps (see **Section A5**), it is unlikely that comparison/control children will enroll in a summer day camp. Thus, there is a high degree of confidence that the comparison/control group will represent weight and fitness outcomes associated with children not attending a summer program.

[figure not shown]

Figure D6. Schedule of school year and summer measurements

Abbreviations—body mass index (BMI), cardiorespiratory fitness (CRF)

D6. Primary and Secondary Measures. Details for implementation of the measurement plan will be finalized in consultation with the CTL Core with respect to training of data collectors, record-keeping procedures, data capture procedures, and construct scoring. For a detailed description of the primary, secondary, covariate, predictor, and determinant measures see Clin-Trls Section 4, Narrative Study Description and Outcome Measures. All measures were selected in consultation with our consultants, the participating school district, and the Recreation Commission. The measures selected 1) represent state-of-the-art techniques that are known to produce valid and reliable data and 2) minimize burden on the participating families.

D6.1. Primary Outcomes (Specific Aim 1). All students enrolled in the study will take part in a cardiovascular fitness (CRF) test (i.e., PACER)[2-8] and have their height and weight measured by trained research staff using standard procedures during a regularly scheduled physical education class. This information will be used to compare changes in BMI (translated into age-sex z-scores [zBMI]) and CRF during summer and the school year. The tests are valid and reliable and used extensively with the proposed age groups.[59-63] Peak height velocity will also be collected as a marker of biological maturation (covariate in statistical models).[1]

D6.2. Secondary Outcomes (Specific Aim 2). Briefly, physical activity, sedentary behaviors, and sleep will be collected using a non-dominant wrist-placed ActiGraph Link for 9-days (common timeframe to collect physical

activity data).[45, 64-74] Children's screen time will be assessed using a parent-proxy report measure completed daily for 9 days by the parent with their child. Parents/children will estimate the total amount of time (hours and minutes) spent in front of a screen that day (e.g., TV, computer, video-game, smartphone, and tablet). [75] Dietary behavior of participants will be estimated using several dietary screeners that have been found to be valid and reliable when compared to multiple pass dietary recall.[76-90]

Table D6. Description of Measures for Primary and Secondary Outcomes and Exploratory Variables at the Child Level

Outcome	Construct	Assessment/Tool	Description/Protocol
Primary	BMI z-score (zBMI)	Height and Weight	Height (cm), weight (kg) w/out shoes or heavy clothing. See Section D6.1. for details
Primary	Cardiorespiratory Fitness	PACER	FITNESSGRAM standardized protocol. See Section D6.1. for details
Secondary	Physical Activity	Accelerometry	Physical Activity (ys). See Section D6.2. for details
Secondary	Sedentary Behaviors	Accelerometry	Sedentary Activity (9-days). See Section D6.2. for details
Secondary	Sleep	Accelerometry	Sleep Activity (9-days). See Section D6.2. for details
		Daily Diary	Daily diary (9-days) completed in evening with help of child (when necessary) report of bed time and wake – See Appendix for details.
Secondary	Dietary Intake	Child Intake of Food/Beverage	Parent report of child past week food/bev intake. See Section D6.2.
Exploratory	Self-regulation (child report)	COMPSCALE – Short Form	The COMPSCALE short form is a 18-item rating scale adapted from the COMPSCALE for children to self-report motives and behavioral inclinations that are linked to socially competence and self-regulation. See Section D6.3.
Exploratory	Self-regulation (classroom teacher and parent report)	COMPSCALE	The COMPSCALE is a 35-item rating scale that adults complete about children. It measures motives and behavioral inclinations that are linked to socially competent and self-regulated children. See Section D6.3.

D6.3. Covariate, Predictor, and Determinant Measures. Participant self regulation will be reported by the classroom teacher and parent/guardian of each child prior to and following each summer.[91] Children will also complete a similar COMPSCALE – Short Form, an 18-item survey that rates their ability to self-regulate.[92] The parent/guardian of each child will also complete a survey that covers rules for bedtime, the home food environment, social support for physical activity, and child dietary intake. Survey questions are from established surveys used to investigate the influence of parents on the health behaviors of their children. To account for environmental factors associated with accelerated weight gain or fitness loss, the obesogenic nature of participating children's/families' neighborhood environments will be assessed using measures that are consistent with other recent, large-scale studies of environmental influences on physical activity and nutrition.[93-96] These measures include walkability (e.g., net residential density, intersection density, land use mix, and retail floor area ratio),[97] the number of parks (and total park acreage) and the number of public (e.g., municipal community center), non-profit (e.g., YMCA), and private (e.g., indoor soccer complex) recreation facilities using publicly-available sources,[93, 94] crime data,[98, 99] neighborhood food,[93, 94, 96] and neighborhood-level disadvantage.[100]

D6.4. Process Implementation Outcomes. Detailed process/implementation data will be captured. Specifically, for each child randomized to the Voucher Program or the comparison/control group, information regarding their attendance at a summer day camp will be collected. For the Voucher Program group in the summer of Y01 and Y02, detailed information will be collected regarding the programmatic offerings occurring at the camps, [101-108] and types of foods and beverages served.[109-112]

D7. Protocol for School and Summer Data Collection. This section describes the protocols for administering the FITNESSGRAM assessments, both H&W and PACER, over a 9-day period during the school year and summer. During the school year children will run the PACER and have their H&W collected during physical education class prior to and following each summer. During this class children will also be provided the activity monitors (ActiGraph), and surveys to take home to their parent for completion. For summer, H&W and PACER will not be collected (see Figure D6.) but monitors and surveys will be distributed during scheduled family days at the child's elementary school (see below for details). During summer and the school year, the parent/guardian will receive text prompts with daily reminders to complete the survey instruments during the 9-day assessment. For the summer, parents/guardians and their child will be contacted in one of two ways. The first primary contact will be through a day-long (8am-5pm) open house at their child's school. Parents/guardians of children participating in the study will be texted two weeks and one week prior about attending a Saturday open house. Parents/guardians showing up to the in-person summer open house will receive \$50 when returning the devices and completed survey packet.

D8. Power Considerations, Statistical Design, and Missing Data. The SDM Core assisted the PI with respect to the analytic plan described in this application. The SDM Core will assist the research team with the codebook (for raw data and constructs), specification of missing data flagging and procedures, data entry/capture, data management, preliminary examination of distributions in preparation for analyses, conduct of statistical analyses, and assistance in interpretation of programming output. All analyses will be completed by the SDM Core, which will have individuals with extensive expertise in the statistical models required for

analyzing the data collected in the proposed project.

D8.1. Power Considerations. Details of the power analysis completed for this study are presented in Clin-Trls Section 4, Statistical Power and Design. Based on the hypothesized difference between z-BMI change for children who receive and do not receive a voucher (i.e., 0.22 vs. 0.11) this study is sufficiently powered.

D8.2. Statistical Models. To test the hypothesis in **Aim 1** and **Aim 2**, repeated measures linear and non-linear mixed models accounting for repeated measures within children and children within schools will be estimated. Group, time, setting (i.e., school vs. summer) and all 2-way and 3-way interactions will be included, with the group-x-time-x-setting interaction as the primary contrast of interest. Structural equation models will also estimate the mediating pathways of the obesogenic behaviors on zBMI change.

D8.3. Sex as a Biological Variable. Because girls and boys have been shown to engage in differing levels of obesogenic behaviors and to have differing levels of fitness and prevalence of overweight and obesity, all models will include sex (i.e., boys vs. girls) and age as covariates. Including sex as a covariate in models will preserve the statistical power of the study while allowing for the examination of sex as a biological variable.

D9. Group Assignment. The unit of randomization will be at the child level. The two conditions will be: 1) Intervention - children receiving a voucher for a summer day camp and 2) Control - no summer day camp voucher. Children will be randomized (using a random number generator) by stratifying them based on grade and gender to ensure equal numbers across the age range and boys and girls in each of the two conditions.

D10. Timeline. A project timeline is provided in Clin-Trls Section 2, Extended Study Timeline.

D11. Limitations and Benchmarks of Success. One key to success will be the study retention of children/families over time. To address this, the measures have been modified based on piloting with comparable individuals and incentives are planned for participation. Another key issue is whether children receiving vouchers attend the day camp during the designated summer. Children in the intervention condition who fail to attend the camp would obviously not be exposed to the independent variable. However, the Recreation Commission has observed that high community demand for summer programming, coupled with ease of access because the camp is centrally located, makes attendance likely. Further, camp attendance (and lack thereof) will be tracked to explore possible barriers to attendance.

D12. Transition to R01-level Grant Submission. The knowledge gleaned from this study will be invaluable to the development or enhancement of existing systems and interventions that support both the physical (weight and fitness), social, and emotional wellbeing children. The study results will provide a foundation for an R01-level grant submission expanding this line of research on interrupting unhealthy weight gain and fitness loss during the summer and continuing to build a foundation for promoting self-regulation to influence both physical health and social-emotional development. This study also has the potential to interrupt a long unstructured period (i.e., summer) in children from low-income households. This could be crucial for helping these children develop self-regulation that could lead to better social, emotional, and behavioral adjustment. The preliminary evidence produced by this study will justify an R01-level study to test the Voucher Program in a large-scale RCT. Should the Voucher Program prove ineffective, this preliminary study will yield detailed process information to inform additional intervention targets for summer programming (e.g., self-regulation). The proposed study will be one of the first to measure self-regulation in addition to all four obesogenic behaviors on the same children during the school year and summer break. Not all of the behaviors in all the children will change in a similar fashion. This study provides initial evidence to suggest patterns of behavior change in groups of children. For instance, activity might substantially decrease in some children without concomitant changes in sleep, diet, or screen time. Other children might show change in more than one of these behaviors, which might nullify the detrimental changes in the other behaviors or interact in unforeseen ways. Further, this study has the potential to produce preliminary data related to the moderating effect of self-regulation on these behavioral pathways. Should self-regulation prove critical, the R01 will incorporate more explicit strategies for targeting self-regulation and more scientifically rigorous measures of the construct. Without this evidence, efforts to mitigate summer weight gain could be misguided, wasteful of resources by unnecessarily targeting all behaviors simultaneously, and less effective than more planned/targeted approaches. Thus, even under conditions of null results, it will be possible to develop more effective strategies for reducing unhealthy weight gains and fitness loss to test in a rigorous well-powered R01

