Title: Preventing Weight Gain and Unhealthy Behaviors in Children

08/08/2019

D8. Power Considerations, Statistical Design, and Missing Data. The SDM Core assisted the PI with respect to the analytic plan described in this application. The SDM Core will assist the research team with the codebook (for raw data and constructs), specification of missing data flagging and procedures, data entry/capture, data management, preliminary examination of distributions in preparation for analyses, conduct of statistical analyses, and assistance in interpretation of programming output. All analyses will be completed by the SDM Core which will have individuals with extensive expertise in the statistical models required for analyzing the data collected in the proposed project.

D8.1. Power Considerations. The power analysis was performed using G*Power (v.3.1.7) to determine the smallest effect detectable assuming a sample size of 80 participants, power of 0.80, correlation between measures of 0.80, and alpha of 0.05. The study is sufficiently powered to detect a Cohens *d* effect size of 0.20, considered a small effect. Previous large scale longitudinal studies of school year vs. summer weight gain,[12, 14, 36] studies that have provided a structured program to children during the summer,[129, 130] and pilot work have shown that the Cohens *d* effect size of the difference between conditions should be approximately 0.50. Children not receiving the Voucher Program are estimated to experience a mean increase in z-BMI of 0.22 over the summer. Conservatively, children in the Voucher Program are estimated to experience half of the gain in z-BMI during the summer of children not in the Voucher Program (i.e., 0.11 increase in z-BMI). The difference between z-BMI change for children who receive a voucher and do not receive a voucher (i.e., 0.22 vs. 0.11) is equivalent to a Cohens *d* of 0.46. However, the power to detect a small effect was chosen to ensure that the study is able to detect the effect of the primary and secondary outcomes.

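### zBMI and CRF are both primary with no rule linking their tests; if either alone can count as success, the chance of a false primary claim is about 7–10%

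*Protocol*

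**What the plan says.** Protocol D6.1 covers the primary outcomes, in the plural, for Aim 1. Of the height, weight and PACER data it says: "This information will be used to compare changes in BMI (translated into age-sex z-scores [zBMI]) and CRF during summer and the school year". Table D6 has two rows marked as primary: zBMI, and cardiorespiratory fitness measured by PACER ("FITNESSGRAM standardized protocol. See Section D6.1. for details").

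Hypothesis 1A (Protocol D2) names both outcomes. It expects that children given camp access "will experience minimal gain in zBMI and loss of fitness during the summer that they receive summer camp access".

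D8.2, in both documents, specifies mixed models for Aim 1 and makes the group-by-time-by-setting interaction the primary contrast. With two primary outcomes, that is one primary test for each.

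The only significance level is in SAP D8.1, among the power inputs: "assuming a sample size of 80 participants, power of 0.80, correlation between measures of 0.80, and alpha of 0.05". It is not divided, and its sidedness is not given. The result is stated as: "The study is sufficiently powered to detect a Cohens *d* effect size of 0.20, considered a small effect". SAP D8.1 adds that power for a small effect was chosen so that the primary and secondary outcomes would be covered. Only zBMI has expected values (0.22 against 0.11, given as d = 0.46).

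The supplied text has no multiplicity adjustment, testing order, joint-success requirement or lead outcome. Further detail is deferred to Clin-Trls Section 4, which was not supplied.

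**The concern.** With two primary tests and no rule joining them, the natural way to run the plan is to test each at 0.05 and report whichever is significant. The error rate for Aim 1 as a whole is then above the level used for each test.

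The plan also does not say what the trial has shown if the two outcomes disagree. Protocol D12 uses the result to decide between a large-scale trial of the vouchers and a search for other intervention targets, so what counts as success matters. A significant PACER result beside a null zBMI result could be presented as primary success, although CRF has no expected change, SD or effect size of its own in the plan.

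**Working it through.** **Inputs.** Two primary outcomes (Table D6); one primary contrast per outcome (D8.2); alpha 0.05, N = 80, power 0.80, correlation between measures 0.80 (SAP D8.1); d = 0.46 for zBMI (SAP D8.1). Assumed: two-sided tests, 40 children per arm (equal numbers, Protocol D9), and a range for the zBMI–CRF correlation. The SAP's 0.80 is a power input for repeated measures. It is not the correlation between these two outcomes.

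**1. The plan's own figure.** The stated d = 0.20 reproduces as a repeated-measures within–between interaction with 2 groups and m = 2 occasions: λ = f²·N·m/(1 − ρ), df = 1 and 78, d = 2f. Solving for 80% power at alpha 0.05 gives f = 0.1003, so d = 0.2006. At d = 0.20, λ = 0.10² × 80 × 2 / 0.20 = 8.0 and power is 79.8%. This uses the whole 0.05 for a single test.

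**2. Chance of at least one false primary result.** Suppose neither outcome has a true effect and either may count as success.

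- Independent tests: 1 − 0.95² = 0.0975.
- Upper bound: 0.05 + 0.05 = 0.10.
- Correlated tests: 1 − P(|Z₁| < 1.96 and |Z₂| < 1.96), bivariate normal.

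| Assumed absolute correlation of the test statistics | Chance of at least one false positive |
|---|---|
| 0 | 9.75% |
| 0.3 | 9.5% |
| 0.5 | 9.1% |
| 0.7 | 8.3% |
| 0.8 | 7.8% |
| 0.9 | 7.0% |

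The figure is 8% or more up to a correlation of about 0.77.

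**3. If both outcomes had to succeed.** With neither effect present, the chance of a false joint claim is 0.10 minus the figure above: 0.25% at correlation 0, 0.93% at 0.5 and 1.65% at 0.7. It cannot exceed 5% even if one of the two effects is real.

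**4. Fixed sequence, zBMI then CRF.** With neither effect present, a false claim needs a false positive on zBMI first, so the rate is 5%. If only zBMI has an effect, a false CRF claim has probability at most 5%. If only CRF has an effect, the only possible false claim is on zBMI, at 5%. zBMI keeps its full alpha.

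**5. Cost of an equal split (0.025 each).** The family-wise error is 1 − 0.975² = 4.94% if independent and 4.65% at correlation 0.5. The loss of power depends on the scale of the effect size:

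| Basis | Power at 0.05 | Power at 0.025 |
|---|---|---|
| Method of step 1, d = 0.20 | 79.8% | 70.6% |
| Method of step 1, d = 0.46 | above 99.9% | above 99.9% |
| t-test on change, d = 0.46 on the single-occasion SD, so 0.46/√(2 × 0.20) = 0.727 on the change SD | 89.5% | 83.1% |
| t-test on change, d = 0.46 on the change SD | 52.9% | 41.4% |

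On the method of step 1, the detectable d rises from 0.20 to 0.22.

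**The case against.** The strongest reply is that the plan breaks no promise. Alpha 0.05 appears once, as a power input, and neither document states an error rate for Aim 1 as a whole. Each test taken singly keeps its 5%. That stands: the gap is an absent rule, and a reader who infers that a stated 5% family-wise rate is false goes beyond the text.

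Hypothesis 1A joins the outcomes with a conjunction. Read as requiring both, the error is at most 5% and needs no adjustment. The wording allows this reading, but it describes expected results, and D8.2 does not turn it into a decision rule. SAP D8.1 speaks of power for the primary and secondary outcomes without mentioning a joint claim. If joint success is intended, it has to be written.

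A reader might also infer that CRF has no power basis at all. The SAP does not support that, since it presents d = 0.20 as covering primary and secondary outcomes. What is missing is a planning value specific to CRF.

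Nor should the fall from 53% to 41% be taken as the cost of splitting alpha. It is one scenario, and the SAP does not say which SD standardizes its 0.46.

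Finally, the study is preliminary to a larger trial, and reporting two distinct prespecified outcomes openly is defensible. This lessens the consequence. It does not say what counts as success when the two disagree.

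**Conclusion.** The point holds in conditional form. Two outcomes are primary, each has its own primary test, the only alpha is undivided, and the supplied text does not say how the tests combine. The chance of a false primary claim is about 7–10% under three conditions: either outcome alone may count as success, neither has a true effect, and the absolute correlation of the test statistics is no more than about 0.9. A flat statement that the rate is 8–10% would be too strong. It drops the first two conditions and needs a correlation of at most about 0.77, on which the documents are silent.

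Applying 0.05 to each test is the natural reading, not an explicit instruction. A rule in Clin-Trls Section 4 would answer the point, but it would still need to appear in the SAP. The sponsor should settle this before analysis, although the preliminary purpose of the study limits the harm.

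**What to change.** In Protocol D6.1, Table D6 and SAP D8.2, state a rule that holds the Aim 1 error at 5%. A fixed sequence fits the plan best, because zBMI has the only planning values, is the target of the mediation models, and matches the trial's title:

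- Test zBMI first, at two-sided 0.05.
- Test CRF confirmatorily at two-sided 0.05 only if zBMI is significant.
- Otherwise report CRF as an estimate with a 95% CI, without a confirmatory claim.

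This is a change of wording, with no extra children or measurements and no loss of power for zBMI. The cost falls on CRF, which cannot be claimed as a confirmed primary result when zBMI is not significant. How often that happens depends on zBMI power. For the two t-test scenarios in the working, the CRF test would be closed with probability 1 − 0.895 = 10.5% or 1 − 0.529 = 47.1%, if the zBMI effect is as assumed.

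If the sponsor wants the outcomes to rank equally, Holm's procedure also holds 5%. Each outcome's power then lies between its values at 0.025 and 0.05. Requiring both to succeed would hold 5% as well, but power for that joint claim would have to be assessed. With either of these, first state the SD to which d = 0.46 refers, since the cost in power depends on it.

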D8.2. Statistical Models. To test the Aims, analytical modeling that capitalizes on the richness of the data set will be utilized. To test the hypothesis in Aim 1, repeated measures linear and non-linear mixed models accounting for repeated measures within children and children within schools will be estimated. Group, time, setting (i.e., school vs. summer) and all 2-way and 3-way interactions will be included, with the group-x-time-x-setting interaction as the primary contrast of interest. For Aim 2, the differences in obesogenic behaviors over time will be evaluated using the same repeated measures linear and non-linear mixed models. Structural equation models will be estimated to evaluate the mediating pathways of the obesogenic behaviors on the amount of change occurring in zBMI over time between the two groups.

D8.3. Sex as a Biological Variable. Because girls and boys have been shown to engage in differing levels of obesogenic behaviors and to have differing levels of fitness and prevalence of overweight and obesity, all models will include sex (i.e., boys vs. girls) and age as covariates. Including sex as a covariate in models will preserve the statistical power of the study while allowing for the examination of sex as a biological variable.

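### Nine-day monitoring windows start from a school-day class in the school year but mainly from a Saturday open house in summer, and the Aim 2 model has no weekday/weekend term, so within-arm summer-versus-school comparisons can be distorted and a weekday camp effect diluted

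*Protocol*

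**What the plan says.** Protocol D6.2 measures physical activity, sedentary behaviour and sleep with a "non-dominant wrist-placed ActiGraph Link for 9-days". Screen time is a "parent-proxy report measure completed daily for 9 days by the parent with their child", and Table D6 adds a nine-day sleep diary.

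Protocol D7 uses a different hand-out occasion in each setting. In the school year it is the physical education class: "During this class children will also be provided the activity monitors (ActiGraph), and surveys to take home to their parent for completion". In summer, "monitors and surveys will be distributed during scheduled family days at the child's elementary school". The main summer contact is an open house, for which parents "will be texted two weeks and one week prior about attending a Saturday open house". D7 announces two ways of contacting families in summer but describes only this one.

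Protocol D5 says that the camps "operate daily (Mon-Fri) for the entire summer".

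For Aim 2, SAP D8.2 says that "the differences in obesogenic behaviors over time will be evaluated using the same repeated measures linear and non-linear mixed models". The listed terms are group, time, setting and their interactions. D8.3 adds sex and age, and Protocol D6.1 adds peak height velocity. Neither document gives a weekday/weekend term, a weighting of day types, a valid-day rule or the first recorded day.

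**The concern.** Nine days is one week plus two days, so the weekend share of a window depends on the day it starts. In this plan the start day is tied to setting: a school day in one, usually a Saturday in the other. With no day-type term, some of any summer-versus-school difference may reflect a different weekday/weekend mix.

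This matters more here than in most trials. The Structured Days Hypothesis (Protocol D1) makes the structure of the day the driver of behaviour, and weekend days have neither school nor camp. The comparisons at stake are Hypothesis 2B, which predicts fewer obesogenic behaviours in the school year, and the setting terms of the model. Separately, because camp runs only on weekdays, a window rich in weekend days gives the voucher effect fewer days on which to appear.

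**Working it through.** The documents give no count of weekend days and no weekend-weekday gap, so there is no figure of the plan's own to reproduce. The power statement in SAP D8.1 plays no part in this point.

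**Inputs.** Window of 9 days (Protocol D6.2). School-year hand-out on a school day, weekday not given (D7). Summer hand-out mainly on a Saturday (D7). Camp Monday to Friday (D5). The first recorded day is not stated, so both plausible rules are shown, each applied to both settings.

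**Step 1: weekend days in nine consecutive days**

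| Hand-out day | Recording starts same day | Recording starts next day |
|---|---|---|
| Mon, Tue, Wed | 2 | 2 |
| Thu | 2 | 3 |
| Fri | 3 | 4 |
| Sat (summer) | 4 | 3 |

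A same-day start gives 4 in summer against 2-3 in the school year. A next-day start gives 3 against 2-4.

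**Step 2: shift in an unweighted nine-day mean.** Let G be the weekend-minus-weekday gap, taken as equal in both settings, and let wS and wY be the weekend days in the summer and school-year windows. The spurious summer-minus-school shift is (wS - wY)/9 x G.

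- Same-day start: (4 - 3)/9 = 0.11 to (4 - 2)/9 = 0.22 of G.
- Next-day start: (3 - 4)/9 = -0.11 to (3 - 2)/9 = +0.11 of G.

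For illustration, assume a screen-time gap of 30 to 90 min/day (not in the documents). The largest shift, 2/9 of G, is then 6.7 to 20 min/day. A shift of 1/9 of G is 3.3 to 10 min/day, in either direction under a next-day start.

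**Step 3: unequal gaps.** Measured against a calendar week with weekend share 2/7, the distortion is (wS/9 - 2/7) x GS - (wY/9 - 2/7) x GY, where GS and GY are the summer and school-year gaps. If summer weekdays are as unstructured as weekends, GS = 0 and only the second part remains. It is +0.06 of GY for wY = 2, -0.05 for wY = 3 and -0.16 for wY = 4. With wY = 2 and the same assumed 30 to 90 min/day, that is about 2 to 6 min/day.

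**Step 4: the randomised contrast.** Add a weekend effect G common to both arms. The summer means are mV + (wS/9) x G for voucher and mC + (wS/9) x G for control. Their difference is mV - mC, free of wS. The same holds in the school year, so the term also drops out of group-by-time-by-setting.

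**Step 5: dilution.** Suppose camp changes behaviour by E on weekdays and by nothing at weekends. The calendar-week effect is (5/7) x E, and the measured effect is (9 - wS)/9 x E.

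- Saturday start: (5/9)/(5/7) = 0.78.
- Sunday start: (6/9)/(5/7) = 0.93.

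**The case against.** Four arguments on the other side deserve weight.

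First, a reader might take 4 against 2-3 weekend days as what the trial will record. The documents do not establish that. It needs recording to begin on the hand-out day, a part-day Saturday (the open house runs 8am to 5pm) to count in full, and every child to come through the open house although a second contact route exists. A next-day start can reverse the sign. This limits what can be said about size. It does not remove the gap, because the plan fixes none of these things.

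Second, a reader might infer that the voucher comparison is biased. It is not: children are randomised individually, D7 gives one hand-out scheme for both arms, and a common weekend effect cancels (Step 4). This stands in full.

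Third, a reader might put the dilution at 5/9 of the effect, or compare 5/9 with the 7/9 of a Monday-to-Thursday start. The first takes a camp day as its reference, and the second borrows a school-year window when no camp is running. Hypothesis 2A concerns behaviour during the summer, so a calendar week (5/7) is the right benchmark.

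Fourth, the full measure descriptions are in a document that is not part of this material, Protocol D6 leaves construct scoring to be finalised, and SAP D8.2 does not say that the outcome is an unweighted mean. Day-level records are therefore not excluded. But a day-level model with only the listed terms would still average over whatever days the window holds, so the stated model does not solve the problem.

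**Conclusion.** The point holds for the within-arm summer-versus-school comparisons (Hypothesis 2B and the setting terms) of accelerometry, sleep and screen time. With an equal gap in both settings and unweighted averaging, the shift is 0.11 to 0.22 of the weekend-weekday gap for a same-day start and -0.11 to +0.11 for a next-day start. The plan does not let a reader say which applies, or even the sign.

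The voucher-versus-control contrast is not biased by this, provided both arms follow the D7 hand-out scheme. It is diluted to 0.78 (Saturday start) or 0.93 (Sunday start) of the calendar-week effect if the camp effect is confined to weekdays. A camp effect that carries into weekends would be diluted less.

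zBMI and PACER are untouched because they are not measured over the window. Dietary intake is a past-week report and is also outside the point. The mediation models use the affected behaviours and inherit the problem to that extent.

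**What to change.** In SAP D8.2, analyse the accelerometry, sleep and screen-time outcomes at day level, with a weekday/weekend term and its interactions with group and setting. Report whole-week estimates standardised to 5 weekdays and 2 weekend days in both settings. The weekday share is then 5/7 everywhere, and the imbalance in Step 2 is zero whatever the start day.

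In Protocol D7, state the first recorded day under one rule for both settings, say how a part hand-out day is treated, and describe the second summer contact route. Record each child's actual start day.

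Report the Monday-to-Friday voucher-versus-control contrast as a supportive analysis. It should not become the main test of 2A: that would change the question from behaviour over the summer to behaviour on camp days, and would miss any compensation at weekends.

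The cost is SAP wording and a few more model terms. No new data are needed, since the monitors and diaries already yield daily records. The downside is some loss of precision from the added interactions in a sample of 80 children.
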